7.4 Patient Disposition

The number of screened patients will be summarized. For screen failures, the reason for screen failure will be summarized using counts and percentages.

The number of enrolled patients will be summarized along with the number and percentage of enrolled patients in the Safety and Efficacy Populations, completing the study, withdrawing from the study and the primary reason for withdrawal, and the number of deaths. Number of patients previously enrolled in PERSEPT 1, PERSEPT 2 and PERSEPT 3 studies will also be summarized. Analyses will be stratified by type of surgery and overall.

7.5 Protocol Deviations

Deviations from the protocol will be recorded in the electronic data capture (EDC) and reviewed on a monthly basis by Medical Monitors. Listing of all protocol deviations will be created.

7.6 Patient Characteristics

7.6.1 Baseline and Demographic Characteristics

All baseline characteristics will be summarized by surgery type and overall for the Safety and Efficacy Population. The analysis will then be repeated stratifying by age group (< 12 years and ≥ 12 years). The following parameters will be summarized:

- Age
- Race
- Ethnicity
- Sex

- Weight at baseline
- Height at baseline
- Body mass index (BMI) at baseline
- Vital Signs (systolic blood pressure [SBP], diastolic blood pressure [DBP], heart rate, etc...) at baseline
- 12-Lead electrocardiogram (ECG) at baseline
- Physical Examination at baseline

No hypothesis testing is planned for baseline characteristics, so the analysis will be purely descriptive.

Listings of baseline characteristics will also be created.

7.6.3 Surgery Characteristics

Surgery characteristics will be summarized by type of surgery and overall. The following characteristics will be included in the summary: predicted type (major or minor), predicted maximum blood loss in a patient without a bleeding disorder who is

undergoing this type of procedure, predicted anesthesia, actual type (major or minor), estimated actual blood loss, actual anesthesia, and surgery complications.

Listing of surgery characteristics will be created.

7.6.4 Prior Medications

Medications will be coded with World Health Organization Drug Dictionary (WHO DD) providing Anatomical Therapeutic Chemical (ATC) 2 and ATC4 codes, and PT for each medication. Number and percentage of patients taking previous bleeding medications and number and percentage of patients taking previous ITI therapy medications will be summarized by type of surgery and overall.

Previous bleeding medications and previous ITI therapy medications will be presented in 2 listings.

7.7 Efficacy Endpoints and Analysis

All the Efficacy analyses will be stratified by surgery type and overall. All analyses will then be repeated stratifying by age group (< 12 years and \geq 12 years). Efficacy population will be used for all the analyses described in this section.

7.7.1 Analysis of Primary Efficacy Endpoint

The primary efficacy endpoint is the percentage of surgical or other invasive procedures with a “good” or “excellent” response to LR769 treatment, as assessed by the investigator at the study center 48 (\pm 4) hours after the last administration of LR769; this assessment will be based upon the totality of assessments performed on the patient at each timepoint, also taking into consideration the surgeon’s intraoperative hemostatic assessment, the number of (interventions for) bleeding episodes, oozing, blood transfusions, and the amount of LR769 used. An additional sensitivity analysis will be performed in which patients whose 48-hour assessment is missing are treated as failures.

The proportion of “good” and “excellent” responses at 48 (\pm 4) hours will be summarized. Clopper-Pearson exact 95% confidence interval for proportion will be calculated for each surgery type and age group and overall. The summaries will include missing assessments in percent calculation, while they will still be discarded when calculating the proportion of successes and the confidence interval (CI). The missing values imputed as per section 7.3 of this SAP will be analyzed as imputed.

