6.13 Removal of Patients from the Trial or Treatment

The investigator may withdraw a patient from the study for any of the following reasons:

- The investigator believes it is in the best interest of the patient to discontinue the study
- The Sponsor or investigator terminates the study
- The patient withdraws consent or requests to be discontinued from the study
- The patient is non-compliant

In case of early withdrawal of the patient, he will be asked to perform the 48 (\pm 4) hour visit assessment after last administration of LR769, unless he has withdrawn Informed Consent.

The investigator may discontinue a patient from LR769 treatment for any of the following reasons:

- AE or SAE possibly related to LR769 treatment
- A clinically significant change in the patient's condition that does not allow safe administration of LR769
- Per judgment of the investigator, if an adequate hemostatic response is not achieved with LR769, and the bleeding requires continued treatment, the treating physician should stop treatment with LR769 and treat the patient with a rescue therapy, such as another bypassing agent (e.g., FEIBA® or NovoSeven®) and/or other effective hemostatic treatment. The patient remains eligible for treatment with LR769 for a new surgical procedure taking into account the pharmacodynamic half-life of the rescue therapy given.

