9.5 Efficacy Endpoints

Efficacy results will be reported as descriptive statistics. Surgeries will be examined overall as well as by major procedures and minor procedures separately.

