9.5.1 Primary Efficacy Endpoint

The primary efficacy endpoint is the percentage of surgical or other invasive procedures with a “good” or “excellent” response to LR769 treatment as assessed by the investigator at the study center 48 (± 4) hours after the last administration of LR769; this assessment will be based upon the totality of assessments performed on the patient at each timepoint also taking into consideration the surgeon’s intraoperative hemostatic assessment, the number of (interventions for) bleeding episodes, oozing, blood transfusions, and the amount of LR769 used.

A point estimate of this endpoint will be calculated together with a Clopper-Pearson exact 95% confidence interval.

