4. SAMPLE SIZE AND POWER CALCULATION

The sample size was determined based on adaptations of international guidelines for coagulation factors and after United States (US) and European Union (EU) health authority consultations. The study will continue until at least 12 surgical procedures (including a minimum of 6 major surgeries, of which at least 5 must be procedures other than central venous access device placement) have been performed in at least 6 patients.

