7. ANALYTICAL PLAN AND STATISTICAL METHODS

7.1 General Conventions and Statistical Considerations

All statistical analyses will be performed and data appendices will be created using the SAS system version 9.4 or higher.

Data collected in this study will be presented in summary tables and patient data listings. Summary descriptive statistics for continuous variables will include the number of observations with non missing values, number of observations with missing values, mean, standard deviation (SD), median, and minimum and maximum values. All raw data will be presented to the original number of decimal places. Means, medians, quartile 1 (Q1), and quartile 3 (Q3) will be presented to 1 more decimal place than in the raw data. Standard deviations will be presented to 2 more decimal places than in the raw data. All data collected will be presented in the data listings.

Summary tables for categorical variables will include the number and percentage of observations for each category. If not specified additionally, the number of observations with non missing values will be the denominator for percentage calculation.

Unless otherwise stated, all statistical tests will be performed using 2-sided tests at the 5% significance level. P-values less than 0.001 will be displayed as <0.001 in the outputs.

Analyses will be stratified by the type of surgery (Minor/Major).

The protocol allows for one patient to enter the study more than one time (for different procedures). Baseline characteristics and demography data will be summarized on a patient level, while efficacy and safety assessments are to be analyzed on a procedure level. Procedure characteristics and disposition will also be summarized on a procedure level. When performing analysis on a patient level, the first value observed for a patient is to be reported (for instance, age that was recorded during the first procedure for the patient will be summarized in the demographics). All tables will contain explicit footnotes to describe on what level the data are summarized.

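### The primary Clopper-Pearson interval assumes independent procedures, but patients may contribute several; with positively correlated outcomes its lower limit can be too favourable, and no patient-level check is planned

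*SAP*

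**What the plan says.** The unit of the primary endpoint is the procedure. Protocol 9.5.1 states: "A point estimate of this endpoint will be calculated together with a Clopper-Pearson exact 95% confidence interval". SAP 7.7.1 extends this to subgroups: "Clopper-Pearson exact 95% confidence interval for proportion will be calculated for each surgery type and age group and overall". SAP 7.7.2 applies the same approach to the success-rate secondary endpoints.

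SAP 7.1 recognises repeat entry, "The protocol allows for one patient to enter the study more than one time", and settles the level of analysis: "efficacy and safety assessments are to be analyzed on a procedure level". It adds that patient-level summaries use the first recorded value and that footnotes will name the level of each table.

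SAP 4 sets the minimum size at 12 procedures, at least 6 of them major, which "have been performed in at least 6 patients". Neither document states a maximum number of procedures per patient. Protocol 6.13 says of a patient who stopped LR769 for inadequate hemostasis and received rescue therapy: "The patient remains eligible for treatment with LR769 for a new surgical procedure".

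The only sensitivity analysis of the primary endpoint (SAP 7.7.1) concerns missing 48-hour assessments. Repeat participation appears in the disposition summary (SAP 7.4): "Number of patients previously enrolled in PERSEPT 1, PERSEPT 2 and PERSEPT 3 studies will also be summarized".

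**The concern.** Clopper-Pearson limits come from the binomial distribution, which requires independent outcomes with a common success probability. Two procedures in one patient share the patient and the underlying disease, and often the site and the unblinded rater. Exclusion criterion 11 itself gives previous non-response to bypassing products as an example of a condition that could affect the outcome, so the protocol treats response as partly a patient trait. If outcomes cluster by patient, 12 procedures carry less information than 12 patients would, and the interval does not reflect this.

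The interval is the planned statement of uncertainty for the primary endpoint of a very small single-arm study. Protocol 9.5 says "Efficacy results will be reported as descriptive statistics", and no threshold or test is attached to it. What is at stake is therefore how precise the result looks, not a type I error.

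**Working it through.** **Inputs from the documents.** At least 12 procedures, at least 6 of them major, in at least 6 patients (SAP 4); two-sided 95% Clopper-Pearson (Protocol 9.5.1, SAP 7.7.1); repeat entry allowed with no stated maximum (SAP 7.1).

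**Assumed.** The within-patient correlation (ICC) is not given. Results are for 0.3 and 0.5, with 0 and 1 as the ends of the range. True success rates p were scanned from 0.60 to 0.96 in steps of 0.005.

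**Step 1: the nominal 95%.** With 12 independent procedures, minimum coverage over the scanned range is 95.5%. The stated level is therefore reproduced under independence.

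**Step 2: coverage with repeats.** Each patient's number of successes is beta-binomial with mean p and the given ICC. The distribution of the total follows by exact convolution over patients. Coverage at p is the summed probability of all totals whose Clopper-Pearson interval contains p.

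| 12 procedures from | Minimum coverage, p 60-96% (ICC 0.3 / 0.5) | Minimum coverage, p 74-96% (ICC 0.3 / 0.5) |
|---|---|---|
| 10 patients, two with 2 | 94.3% / 93.5% | 96.9% / 96.5% |
| 8 patients, four with 2 | 93.1% / 91.2% | 96.3% / 95.4% |
| 6 patients, 2 each | 91.7% / 88.5% | 95.6% / 94.4% |
| 6 patients: 7,1,1,1,1,1 (extreme but permitted) | 83.1% / 75.3% | 90.0% / 85.8% |

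For six patients with two each, the minimum occurs near p = 73%.

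**Step 3: error of the lower limit.** The chance that the lower limit lies above the true rate should be at most 2.5%. With six patients having two each, it reaches 4.6% / 6.7%.

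**Step 4: all 12 procedures succeed.** Under independence the lower limit solves p^12 = 0.025, giving p = 0.025^(1/12) = 73.5%.

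For a patient with two procedures, P(both succeed) = p[p + ICC(1 - p)]. For six such patients the lower limit solves {p[p + ICC(1 - p)]}^6 = 0.025, that is (1 - ICC)p^2 + ICC·p = 0.025^(1/6) = 0.5407.

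- ICC 0.3: 0.7p^2 + 0.3p = 0.5407, so p = 69.0%.
- ICC 0.5: 0.5p^2 + 0.5p = 0.5407, so p = 65.4%.
- ICC 1: p = 54.1%, the same as 6 successes in 6 patients.

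**Step 5: all 6 major procedures succeed, in three patients with two each.** The planned limit is 0.025^(1/6) = 54.1%. With correlation, (1 - ICC)p^2 + ICC·p = 0.025^(1/3) = 0.2924, giving 46.7% (ICC 0.3) and 41.4% (ICC 0.5).

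**The case against.** The strongest reply is that the problem is confined to a narrow range. With 12 procedures the largest possible lower limit is 73.5%, so it cannot lie above a true rate of 74% or more, whatever the layout or ICC. Any miss there comes from the upper limit being too low, which does not flatter the product. With six patients having two procedures each, coverage at a true rate of 90% is 98.8% / 98.3% for ICC 0.3 / 0.5, and with 8 or 10 patients it stays above 95% throughout 74-96%. Protocol 1.1 quotes response rates of about 90% and 92% for factor VIIa, although for bleeding episodes rather than surgery.

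Further, 12 procedures and 6 patients are minimums, the ICC is assumed, and exclusion criterion 11, with eligibility confirmed before each procedure (Protocol 7.2.1), may limit repeat failures. SAP 7.1 already requires level footnotes and full listings, and the table shells are a separate document that was not available. A first-procedure analysis also discards data and estimates a somewhat different quantity.

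All of this is correct, and it limits the size of the problem. It does not remove it. The true rate is what the study is meant to estimate, so the interval should not depend on that rate being high. The smaller major-procedure stratum is affected as well. Footnotes and listings let a reader notice repeats, but they do not change the interval or say that it assumes independence.

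**Conclusion.** The concern holds in its conditional form: if patients contribute several procedures with positively correlated outcomes, the interval is not exact and its lower limit can be too favourable. The plan permits this, and at 12 procedures in 6 patients repeats are unavoidable.

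At ICC 0.3-0.5 and that minimum, with two procedures per patient, the cost is roughly 3 to 7 percentage points of worst-case coverage (95.5% to 91.7% or 88.5%). For 12 of 12 successes it is 4.5 to 8.1 points on the lower limit (73.5% to 69.0% or 65.4%). It is larger with one heavily repeating patient, small with few repeats, and absent with none. The procedure-level point estimate is not put in question.

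The conclusion rests on an assumed ICC and on finding neither a per-patient maximum nor a patient-level efficacy analysis in the protocol or SAP. The SAP should be changed, but the study's main result is not invalidated.

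**What to change.** Keep the procedure-level estimate and the planned Clopper-Pearson interval, and make three additions for the primary and success-rate secondary endpoints:

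1. State in SAP 7.7.1 and in the table footnotes that the interval assumes independent procedures.
2. Print the number of patients beside the number of procedures in every success-rate table.
3. Pre-specify a sensitivity analysis applying Clopper-Pearson to each patient's first procedure, overall and by age group. Within each surgery type, use the patient's first procedure of that type. Each patient then counts once, so the interval is valid without an ICC. It also matches the first-value rule that SAP 7.1 already uses for patient-level summaries.

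Do not replace the primary interval with one based on an estimated design effect; so few patients cannot support a usable ICC estimate.

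The cost is a short SAP update, one sensitivity table and one extra count. Because the primary method is unchanged, the condition in SAP 7.1 for a protocol amendment should not apply. The drawback is that later procedures are left out and the supporting interval is wider. If every first procedure succeeds, its lower limit is 0.025^(1/n): 54.1%, 63.1% or 69.2% with 6, 8 or 10 patients, and only 29.2% in a stratum of three patients. It should be presented as support for the main interval, not a replacement.

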7.7.2 Analysis of Secondary Efficacy Endpoints

The following endpoints are considered secondary for this study:

- Percentages of success as defined as the combination of “good” and “excellent” responses by the investigator or designee for all efficacy timepoints other than the primary
- Percentages of “poor,” “moderate,” “good,” and “excellent” response by the investigator or designee for all efficacy timepoints
- Percentages of success as defined as the combination of “good” and “excellent” responses by the surgeon/practitioner for the intraoperative period
- Percentages of “poor,” “moderate,” “good,” and “excellent” response by the surgeon/practitioner for the intraoperative period
- Intraoperative blood loss determined by the surgeon/practitioner as compared to the surgeon/practitioner’s maximum predicted blood loss
- Number of events requiring transfusion between start of procedure and 48 (±4) hours after last administration of LR769
- Changes in hemoglobin between start of procedure and 48 (±4) hours after last administration of LR769
- Amount of LR769 used. Total, and separated by use in hospital, at home, or for specific reasons (eg, physical therapy, or other reasons like drain or suture removal)
- Number and type of bleeding episodes at the surgical site between start of procedure and 48 (±4) hours after last administration of LR769
- Number of surgical interventions/re-explorations for bleeding episodes between start of procedure and 48 (±4) hours after last administration of LR769

The first four secondary endpoints will be analyzed similarly to the primary endpoint: numbers and percentages of successes will be summarized at each timepoint, together with their Clopper-Pearson exact confidence limits.

Difference between the expected and actual blood loss will be calculated for each surgery in the study and then summarized together with 95% confidence limits. Number of events requiring transfusion, Number of bleeding episodes (by type) at the surgical site between start of procedure and 48 (±4) hours, and Number of surgical interventions/re-explorations for bleeding episodes between start of procedure and 48 (±4) hours after last administration of LR769 will be analyzed similarly.

Hemoglobin levels will be summarized at baseline and at 48 (±4) hours after last administration of LR769. Changes from baseline will also be summarized for 48 (±4) hours timepoint. 95% confidence limits for the changes will be displayed.

Total amount of study drug administered per surgery will be summarized. A summary will be created for total amount administered per surgery, total amount administered in the hospital, and total Amount administered at home. Additionally, a separate summary will be created for total amount administered by indication.

Data listings of postoperative response assessments, transfusions, surgical interventions or invasive procedures, and bleeding episodes will be created.

7.8 Exposure and Safety Endpoints and Analysis

All the analyses in this section will be stratified by surgery type and overall, and then by age group (< 12 years and ≥ 12 years). The Safety population will be used for all the analyses described in this section.

7.8.1 Exposure to Study Treatment

The exposure analysis is a part of the secondary efficacy endpoint analysis in this study (Section 7.7.2). Tables described in this section will be generated in addition to the ones specified in section 7.7.2.

The total amount of study drug taken by patient (µg/kg and total mass [mg]), total duration of treatment (days), and the number of administrations per patient will be summarized.

A data listing of exposure to LR769 will be created.

7.8.2 Adverse Events

All AEs will be coded using MedDRA (Version 15.0). An AE will be considered a treatment-emergent adverse event (TEAE) if it occurred or worsened after the first dose of study drug. In case a patient undergoes multiple procedures in the study, the TEAE will be assigned to the latest procedure prior to the event itself. Non-TEAEs are AEs occurring after signing Informed Consent but before the first administration of study drug. TEAEs will be summarized for the Safety Population. Non-TEAEs will be summarized for all enrolled patients.

The number and percentage of patients as well as the number of events will be summarized for any TEAEs, any treatment emergent SAEs, any treatment-related TEAEs, any non-treatment-related TEAEs, any TEAEs leading to discontinuation from the study, any TEAEs leading to study drug withdrawal and any TEAEs resulting in death. Summaries will be done stratifying by SOC and PT. An AE will be considered treatment related if it has a definite, probable, or possible relationship to the study treatment or if the relationship to the study treatment is missing. Additionally, a summary of TEAE's by SOC, PT, and severity grade will be created.

Separate summaries and listings will be provided for treatment-emergent thromboembolic events and allergic and anaphylactic reactions.

A data listing of TEAEs will be produced. Separate listings will also be prepared for SAEs, AEs leading to death, TEAEs leading to discontinuation from the study, TEAEs

leading to study drug withdrawal, thromboembolic AEs, and allergic and anaphylactic AEs. A listing of deaths will be provided as well, including information about the primary reason for death.

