5.2.2 Treatment for Major Surgical Procedures

The initial dose of LR769 (200 µg/kg) will be followed by repeated administration of 75 µg/kg of LR769 every 2 hours (±5 minutes) for the first 48 hours after completion of the procedure. The minimum duration of LR769 treatment for major procedures will be 5 days, according to the frequency listed in the [table below](#).

Table 1. Dose(s) and Dosing Schedule(s) for Major Surgical Procedures

Day	Dose	Recommended Frequency
Day 0 (within 2 minutes of surgical incision or invasive procedure)	200 µg/kg	Initial dose
Day 0 (post first dose) – 48 hours	75 µg/kg	Every 2 hours (±5 minutes)
Days 3- 4	75 µg/kg	Intervals of up to every 4 hours but not more frequently than every 2 hours
Days 5-6	75 µg/kg	Intervals of up to every 6 hours but not more frequently than every 2 hours
Days 7-10	75 µg/kg	Intervals of up to every 8 hours but not more frequently than every 2 hours
Day 11 to Last Administration of LR769	75 µg/kg	Intervals of up to every 12 hours but not more frequently than every 2 hours

NOTE: If clinically indicated because of oozing or similar findings suggesting the need for more frequent LR769 infusions, the treatment interval may be shortened in consecutive doses within the guidelines stated in Table 1.

If the patient requires further treatment with LR769 after hospital discharge, the patient will administer LR769 at home according to the investigator’s judgment and the dosing guidelines specified in Table 1. The patient will be provided with LR769 and directions for its storage, reconstitution and administration along with a patient diary in which to record LR769 administration.

If physical therapy is planned, an IV bolus dose of 75 µg/kg of LR769 administered within ≤2 minutes is recommended each time before the therapy begins. Similarly, before drain or suture removal, an IV bolus dose of 75 µg/kg of LR769 administered within ≤2 minutes is recommended.

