7.2 Surgery/Invasive Procedure and LR769 Treatment

7.2.1 Before Surgery/Invasive Procedure

- Confirm eligibility
- Physical examination (excluding height, including weight, which is the weight to be used for calculating dose of LR769) within 24 hours before the procedure
- An IV bolus dose of 75 µg/kg (for a minor surgery or other minor invasive procedure) or 200 µg/kg (for a major surgery or other major invasive procedure) of LR769 administered within ≤2 minutes before the surgical incision or start of the invasive procedure.
- Predicted surgery/invasive procedure characteristics
- Vital signs (blood pressure, heart rate, respiratory rate, and body temperature [sublingual or tympanic])
- Assessment of concomitant medications
- Assessment of AEs
- Immunogenicity sample (including storage serum sample for future use)

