3.2.1 Treatment for Major Surgical Procedures

The initial dose of LR769 (200 μ g/kg) will be followed by repeated administration of 75 μ g/kg of LR769 every 2 hours (\pm 5 minutes) for the first 48 hours after completion of the procedure. The minimum duration of LR769 treatment for major procedures will be 5 days, according to the frequency listed in the table below.

Table 1. Doses and Dosing Schedule for Major Surgical Procedures:

Day	Dose	Recommended Frequency
Day 0 (before surgical incision or invasive procedure)	200 μ g/kg	Initial dose
Day 0 (post first dose) – 48 hours	75 μ g/kg	Every 2 hours (\pm 5 minutes)
Days 3- 4	75 μ g/kg	Intervals of up to every 4 hours but not more frequently than every 2 hours

Days 5-6	75 µg/kg	Intervals of up to every 6 hours but not more frequently than every 2 hours
Days 7-10	75 µg/kg	Intervals of up to every 8 hours but not more frequently than every 2 hours
Day 11 to Last Administration of LR769	75 µg/kg	Intervals of up to every 12 hours but not more frequently than every 2 hours

NOTE: If clinically indicated because of oozing or similar findings suggesting the need for more frequent LR769 infusions, the treatment interval may be shortened in consecutive doses within the guidelines stated in Table 1.

If the patient requires further treatment with LR769 after hospital discharge, the patient will administer LR769 at home according to the investigator's judgment and the dosing guidelines specified in Table 1. The patient will be provided with LR769 and directions for its storage, reconstitution and administration along with a patient diary in which to record LR769 administration.

If physical therapy is planned, an intravenous (IV) bolus dose of 75 µg/kg of LR769 administered within ≤2 minutes is recommended each time before the therapy begins. Similarly, before drain or suture removal, an IV bolus dose of 75 µg/kg of LR769 administered within ≤2 minutes is recommended.

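### SAP 7.8.2 assigns a TEAE by procedure although each LR769 course starts before its procedure, so an event between the initial dose and incision of a repeat course can be credited to the earlier procedure

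*SAP*

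**What the plan says.** SAP 7.8.2 calls an adverse event treatment-emergent "if it occurred or worsened after the first dose of study drug". For a patient with several procedures it then says that "the TEAE will be assigned to the latest procedure prior to the event itself". The SAP change log gives multiple enrolment of the same patient as the reason for this rule.

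The rule matters because of three other provisions:

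- **Repeat entry.** SAP 7.1: "The protocol allows for one patient to enter the study more than one time (for different procedures").
- **Unit of analysis.** SAP 7.1: "efficacy and safety assessments are to be analyzed on a procedure level".
- **Strata.** SAP 7.8: "All the analyses in this section will be stratified by surgery type and overall".

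The initial dose comes before the procedure, but the interval is worded differently from place to place:

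- Protocol 7.2.1: "administered within ≤2 minutes before the surgical incision or start of the invasive procedure". The 2 minutes can be read as injection time or as lead time.
- Protocol 5.2.2, Table 1 (major): "Day 0 (within 2 minutes of surgical incision or invasive procedure"). Protocol Table 2 and SAP Table 2 (minor) say the same.
- SAP 3.2.1, Table 1 (major): "Day 0 (before surgical incision or invasive procedure"), with no limit.

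**The concern.** Two adjacent rules run on different clocks. Dosing decides whether an event is treatment-emergent, and the procedure decides which course it belongs to. In a repeat course the dose comes first. An event in the interval before incision therefore has the previous procedure as its most recent one.

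If the two procedures differ in type, the event lands in the wrong stratum. The initial dose is 200 µg/kg for major and 75 µg/kg for minor procedures, so the major/minor split is also a split by initial dose. Protocol 6.9.9 asks for particular attention to allergic reactions after the initial administration, and such reactions can begin in this interval.

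**Working it through.** The documents give no figure for adverse event attribution, so there is nothing to reproduce. The check applies the rule to a constructed patient and then sizes one moved event.

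**1. Which onsets move.** Assumptions: procedure 1 is minor; procedure 2 is major and 60 days later; the second course's initial dose is given 2 minutes before incision; the operation lasts 120 minutes. Each event goes to the procedure with the latest anchor time at or before onset. Onset is in minutes relative to incision 2.

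| Onset | Anchor: procedure start | Anchor: procedure completion | Anchor: first dose of course |
|---|---|---|---|
| -1.5 | 1 (minor) | 1 (minor) | 2 (major) |
| -0.5 | 1 (minor) | 1 (minor) | 2 (major) |
| 0.5 | 2 (major) | 1 (minor) | 2 (major) |
| 5 | 2 (major) | 1 (minor) | 2 (major) |
| 30 | 2 (major) | 1 (minor) | 2 (major) |
| 130 | 2 (major) | 2 (major) | 2 (major) |

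With procedure start as anchor, only the two onsets before incision go to the wrong course. With completion as anchor, the tested intraoperative onsets do too. SAP 7.8.2 does not name the anchor; SAP 7.2 uses procedure completion for a different purpose, the postoperative timepoints. The dose anchor places every tested onset correctly.

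**2. Procedure read as enrolment.** Protocol 6.1 counts a patient as enrolled at consent, and Protocol 7.1 puts screening at Days -21 to -1. An event during screening for a second enrolment, after the first course was dosed, could then be assigned to a course not yet dosed. This reading closes the gap before incision but opens another.

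**3. Cancellation.** Suppose the reaction leads to the second procedure being cancelled. The rule covers patients who undergo several procedures. With one earlier procedure, the patient has had only one, and the rule does not apply on its own terms. With two or more, it leaves the event with an earlier one. Neither outcome credits the course that was dosed.

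**4. Courses exposed.** The design minimum is 12 procedures in 6 patients (SAP Section 4). If both minima are met exactly, 12 - 6 = 6 courses are repeats. With 12 different patients there are none.

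**5. Size of one moved event.** Assume 6 major and 6 minor procedures, with procedures as the denominator as in SAP 7.1. Clopper-Pearson 95% limits are shown for scale only:

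- 0/6: upper limit 1 - 0.025^(1/6) = 45.9%.
- 1/6: 16.7%; lower limit 1 - 0.975^(1/6) = 0.4%; upper limit, the 97.5% point of Beta(2, 5), = 64.1%.
- Overall, 1/12 = 8.3% (0.2 to 38.5%) under either rule.

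The correct table reads major 1/6 and minor 0/6; the literal rule gives major 0/6 and minor 1/6.

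**The case against.** The strongest reply is that the SAP uses procedure to mean the whole enrolment. SAP 7.1 speaks of the age recorded during a patient's first procedure, although demographics are taken at screening, and the change log refers to multiple enrolment. On that reading a dose given before incision already belongs to its own procedure. The reading is plausible, but SAP 7.8.2 does not state it, and it has the screening problem shown above.

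The reply on size stands. Misassignment needs a repeat patient and an onset in a short interval, and a change of stratum also needs two procedures of different type. SAP 7.8.2 plans counts and percentages for adverse events, not confidence intervals. Allergic and anaphylactic reactions have their own summaries and listings (SAP 7.8.2), are reported on the serious-event timeline even when not serious (Protocol 6.9.9), and stop the study pending investigation (Protocol 6.12). Such a case would be examined individually.

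A reader might infer three stronger claims that the documents do not support:

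- **That every reaction to the initial dose of a repeat course is misassigned.** With procedure start as anchor, an onset after incision is assigned correctly.
- **That an event before incision in a first course belongs nowhere.** Only one course exists to hold it, so there is no practical error.
- **That an event leading to cancellation stays with the earlier procedure for good.** For a patient with one earlier procedure the rule does not apply, and the SAP is silent.

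**Conclusion.** The point holds as a minor defect of wording. Taken literally, SAP 7.8.2 credits an event between the initial dose and the start of a repeat procedure to the earlier procedure, possibly in the other surgery-type stratum. The unstated anchor leaves room for a wider error if completion is used.

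The consequence is limited to the stratified descriptive safety tables. One moved event changes major from 1/6 (16.7%) to 0/6 and leaves the overall 1/12 as it is. That rests on an assumed 6/6 split and a minor-then-major sequence; the documents give no event rate. A reader might also infer that a reaction could go unnoticed. The listings, the reporting rule and the stopping rule speak against that.

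**What to change.** Replace the sentence in SAP 7.8.2 with: *each TEAE is assigned to the enrolment (planned procedure) whose first LR769 dose is the latest before onset of the event, whether or not the procedure then took place.* This settles the anchor and the cancellation case, and it puts attribution on the same clock as the TEAE definition.

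The cost is one sentence and one derivation. Protocol 6.9.1 already records the start date and time of adverse events. The documents do not state outright that in-hospital dose times are captured, so this should be confirmed. SAP 7.3 imputes dates but not times, so an event on the day of dosing with no onset time stays ambiguous under any rule.

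Separately, the sponsor should reconcile the wording on the timing of the initial dose relative to incision in Protocol 5.2.2 and 7.2.1 and SAP 3.2.1 and 3.2.2.
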